##### **b. Exclusion criteria:**

- Terminal ill

#### **6. Risks, side effects and disadvantages in the short and long term**

In the study, no serious adverse events or risks are expected. All participants participate voluntarily and can withdraw from the study at any time. The research group can withdraw a participant at any time if there is a concern for the participant's well-being. A nurse at each of the nursing homes is included in the project and will be present during all data collection periods. The nurses will be involved immediately if any health issues or concerns about health issues should arise. Data on participants who withdraw will be documented.

This project meets the guidelines of the Declaration of Helsinki II, as well as the guidelines of the Regional Ethics Committee.

The research project has been submitted to the Science Ethics Committees for Region Zealand j.nr.: EMN-2021-07672 and is exempt from the obligation to notify.

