### **b. Short literature review and bibliography**

The aging population is increasing both globally (1) and nationally (2). Concurrent with the generally rapidly increasing incidence of overweight (3), a large number of older people risk facing a number of health problems associated with overweight and obesity (Ow/O) (1). Ageing related to malnutrition or undernutrition have received a lot of attention. However, overnutrition described as Ow/O is also classified as a nutritional disorder or a nutrition related condition, in the same term as malnutrition (18).

Today, all older adults in Danish nursing homes are offered an enriched diet type for malnourished older adults, focused on energy dense snacks and a high fat percentage (4). This is not necessarily an appropriate diet, but it is unknown which nutritional interventions that are effective in maintaining/ improving physical functioning, independency and quality of life. One of the concerns is that many older adults with Ow/O may have loss of muscle mass, which can worsen with weight loss (5–9), if this is not taken into account in the nutritional intervention. There is therefore a clear need to develop targeted interventions for older adults with Ow/O that can maintain or improve physical functioning and quality of life under Danish conditions with the Danish dietary tradition.

However, a literature review of interventions within the last 10 years shows that none of the interventions are aimed at healthy older adults  $\geq 65$  years with a  $\text{BMI} \geq 25\text{kg/m}^2$  and good physical functioning. Instead, interventions targeted older adults with Ow/O with either low physical functioning or chronic diseases. These interventions show that older adults can lose weight, but without significant positive effects on functioning and quality of life (10–16). However, interventions aimed at the target group for this project, which has both reduced muscle function and chronic disease, that nutrition and physical activity interventions have a positive effect on physical functioning (17–22) and quality of life (18,21,22). The interventions in the studies contain complex nutrition and exercise interventions, and the differences in the

intervention descriptions and target groups make it difficult to compare and point to safe and effective interventions.

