#### Intervention

The intervention is developed with a focus on nutritional needs and physical activities.

In follow-up, the PDSA model (25,26) is used to redefine issues and relevant actions together with care staff, the nursing home management and participants. The intervention will be developed on

the basis of new knowledge from sub-study 1, previous studies, practical experiences, the participant's experiences and wishes as well as the staff's experiences and wishes. Together they will be form an implementation catalog, from here, the nursing homes can select a relevant number of components, which will be tested and implemented in practice. An example could be that the general offer of diet type at the nursing home is changed to the diet type "normal" diet for older adult with a high protein content instead of enriched diet type for malnourished older adults (4). Whether the participants are at nutritional risk is assessed by Ernæringsvurderingsskemaet (EVS), and the participants who need a enriched diet or special diet forms such dysphagia diet (4), is of course offered / continues these diets . However, it may be that some participants can achieve / maintain a better physical function with a normal diet.

The implementation duration is 6 months and the PDSA model (25,26) repeated at two-month intervals to strengthen and qualify the intervention. The PDSA model is known to the city's staff in advance, and is additionally used in connection to continuing education. In addition, every day physical activities that contributes to maintaining / improving physical functional is included, based on the potentials that are uncovered in sub-study 1.

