#### All outcome measures

Data are collected at baseline and 6 months (m). The starting point is the same measurements as described in sub-study 1, combined with feasibility in practice.

The data analysis takes into account that not all participants are included in all measurements.

Tabel 1: Data collection in sub study 2

Variable	Method	Baseline	6 m
Age and sex	Journal data	x	
Weight	Calibrated standard weight as part of routinely weighing, Journal data	x	x
Weight, fat%, fat mass (kg), muscle mass (kg), bone mass (kg), BMI, total body water (TBW), TBW%, intracellular water and extracellular water	BIA	x	x
Calf circumference	Measured by non-elastic plastic tape		
Height	Journal data	x	
Height measured	Measured standing or lying	x	
Chronic disease, diagnosis and number	Journal data	x	
Muscle function	30 s CST , gait speed and HGS	x	x
Nutritional risk	EVS	x	x
Quality of Life	ASCOT questionnaire	x	x

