#### 14. Ethics

**a. Why risks, neither in themselves nor in relation to the benefits of the trial, are unjustifiable**

Participation in the project is not associated with minor risk. This project meets the guidelines of the Declaration of Helsinki II, as well as the guidelines of the Regional Ethics Committee. The research project has been submitted to the Science Ethics Committees for Region Zealand j.nr.: EMN-2021-07672 and is exempt from the obligation to notify.

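### The protocol plans no adverse-event data and no weights between baseline and 6 months, so events and weight loss within the period cannot be reported by arm

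*Protocol*

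**What the plan says.** **Risk.** Section 6 says that "In the study, no serious adverse events or risks are expected". Section 14.a says that "Participation in the project is not associated with minor risk". The literature review (section 2.b) gives as a concern that "many older adults with Ow/O may have loss of muscle mass, which can worsen with weight loss", where the nutritional intervention does not allow for it. It adds that differences between earlier studies "make it difficult to compare and point to safe and effective interventions".

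**Intervention.** Homes choose components from a catalogue. One illustration reads: "An example could be that the general offer of diet type at the nursing home is changed to the diet type" for older adults with a high protein content, in place of the enriched diet. Nutritional risk is assessed with the EVS form, and a participant who needs an enriched or special diet "is of course offered / continues these diets".

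**Data.** Table 1 (All outcome measures) schedules weight, bioimpedance body composition including muscle mass, EVS, muscle function and ASCOT at baseline and 6 months. It lists no adverse event of any kind. Section 9 allows the principal investigator to transfer only the information already listed from the journal system (CURA). Section 6 provides for a nurse at each home to be involved if health issues arise, and for data on withdrawn participants to be documented.

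**Analysis.** Section 4 plans ANCOVA, and also Kaplan-Meier and regression methods for repeated measurements over time of physical functioning, weight, muscle mass and quality of life.

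**The concern.** The trial changes nutrition and activity for nursing-home residents, and terminal illness is the only exclusion. Over 6 months some residents may fall, be admitted to hospital, die or lose weight. The protocol gives no route by which such events enter the dataset by arm.

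The gap bears on what the trial can conclude. Section 13 intends an implementation catalogue and best-practice guidelines for use in other Danish cities. A 6-month comparison of weight and muscle mass describes only residents who are present and measured at 6 months. If residents who did badly are more likely to have died or left, that comparison may miss the harm of most interest, and nothing scheduled would show it.

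This is not a matter that a statistical analysis plan can settle later. Such a plan chooses how to analyse data; it cannot analyse variables that the protocol keeps out of the dataset.

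**Working it through.** The protocol gives no figure for harms, so there is none to reproduce. The check sets the sections side by side and then sizes the gap under stated assumptions.

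**1. What Table 1 can and cannot show by arm**
- Weight, muscle mass, nutritional risk, chair stand, gait speed and grip strength: change from baseline to 6 months, among those measured.
- Weight between those points: not scheduled. The routine weighing named as the source in Table 1 may well produce such values, but they are not extracted.
- Falls, hospital admissions, deaths: no row.
- Withdrawals: documented under section 6, with no mention of date or reason.

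**2. Whether another section fills the gap**
- The nurse provision in section 6 is a response in care. It defines no event, form or time window.
- Section 9 restricts journal transfer to the listed information, and no section lists events. Its general statement that data on each participant are documented continuously names no additional variable.
- Section 12 allows journal data to be used when a participant declines a test. That protects the listed variables and adds none.

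**3. Section 4 against Table 1**
- Kaplan-Meier needs an event and its date. Table 1 has neither. Withdrawal is the only candidate, and only if its date is recorded.
- The repeated measurements of weight over time reduce in Table 1 to one baseline and one follow-up value.

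**4. Risk statements**
- Section 6 expects no serious adverse events or risks. Taken literally, section 14.a does not say the same, and its intended meaning is unclear.
- The literature review names a way in which harm could arise.

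**5. Size**

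Inputs: about 100 participants, with three homes in each arm (Sample size calculation; section 3.c), so 100 / 2 = 50 per arm. The 6-month risks r are assumptions; the protocol gives none.

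Chance of at least one event in an arm = 1 − (1 − r)^50:
- r = 2%: 1 − 0.98^50 = 63.6%
- r = 5%: 1 − 0.95^50 = 92.3%
- r = 10%: 1 − 0.90^50 = 99.5%

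Power to compare assumed risks of 5% and 10% (normal approximation, two-sided 5%, clustering ignored):
- SE = √[(0.05 × 0.95 + 0.10 × 0.90) / 50] = √0.00275 = 0.0524
- z = 0.05 / 0.0524 − 1.96 = −1.01, so power is about 16%

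If no event were seen among 50, the one-sided 95% upper limit would be 1 − 0.05^(1/50) = 5.8%, again ignoring clustering. Positive correlation within the six homes would make both figures less favourable.

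**The case against.** A reader might infer that safety cannot be compared between arms at all. The documents do not support that. Weight development is a secondary outcome, and weight, muscle mass, nutritional risk and muscle function are measured in both arms at 6 months. The harm that the protocol names is therefore comparable among those measured.

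A reader might also infer that the literature review contradicts section 6 outright. It does not strictly do so. The muscle-loss concern is conditional on the intervention ignoring it, and section 6 states what is expected. The diet change is only an example, its replacement is described as high in protein, no weight-loss goal is set, and those who need enriched or special diets keep them. The remark about safe interventions says that differing studies make this difficult to judge; it reports no safety signal.

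It can fairly be added that a nurse is on hand, that withdrawals are documented, and that a separate data management plan, not shown, follows Good Clinical Practice. The study is also a non-drug feasibility trial, for which a formal monitoring scheme could be out of proportion. Finally, event counts from 50 residents per arm would not support a test, and the chances of at least one event do not show otherwise.

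All of this limits the point without removing it. The provisions limit exposure or guide care, but they do not put events or dates into the dataset. Low power is a reason to report counts descriptively, not a reason to leave them uncollected.

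**Conclusion.** The point holds in a limited form. The protocol plans no adverse-event data and no weights between baseline and 6 months, and it restricts journal transfer to what is listed. Events and weight loss within the period therefore cannot be reported by arm. Residents who die or leave early contribute no scheduled outcome or event data beyond the documentation of withdrawal. The 6-month comparison of weight and muscle mass stands, but only for those still measured. The Kaplan-Meier and repeated-measurement analyses in section 4 have no matching data in Table 1.

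Under the assumed risks of 2% to 10%, at least one event in an arm is more likely than not (64% to over 99%), while power for a difference such as 5% against 10% is about 16%. What is lost is a description of harms by arm, not a powered safety test.

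This rests on reading the journal restriction in section 9 as referring to the variables in Table 1, and on the unseen data management plan and participant information not adding event data. The point is a worthwhile, inexpensive improvement and does not invalidate the design.

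**What to change.** - Add to Table 1, for both arms and from the CURA journal: routine weights recorded between baseline and 6 months, falls, hospital admissions, and the date of and reason for death or withdrawal.
- Widen the list of transferable data in section 9, and the consent wording, to match.
- State that these data are reported descriptively by arm, with no claim of power for a safety comparison.
- In section 4, name the event and date that the Kaplan-Meier analysis uses and the measurement occasions behind the repeated measures, or remove those analyses.
- Reconcile the risk statements in sections 6 and 14.a with each other and with the concern in the literature review.

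No change of diet or clinical rule is proposed. A review of pooled weights at the two-month PDSA cycles is not needed: pooling would dilute a loss confined to one arm, and the cycles belong to the implementation of the intervention.

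The cost is modest extra extraction time from a system already in use, a few table rows, and an update to the consent form or data agreement.

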#### **7. No biological material are collected.**

#### **8. Information from patient records**

- a. It must be stated which information is needed and what the information is to be used for. There shall distinguish between information to be used before the subjects have given their consent to participate, eg in connection with identification / recruitment, and the information to be used for the project after consent to participation is given.

- b. It must be stated that the information to be used in the project before consent has been given from the subjects, are passed on to the researcher.
- c. It must be stated that the consent gives the person responsible for the experiment, the sponsor and the sponsor's representatives as well any control authority direct access to obtain information in the patient's medical record, etc., including electronic medical records, in order to view information on the subject's health status, which are necessary as part of the implementation of the research project as well as for control purposes, including self-monitoring, quality control and monitoring, which they are obliged to perform.

See appendix 1: Participant information

## **9. Processing of personal data in the project:**

### **a. Data Protection Regulation and the Data Protection Act are complied with.**

In sub-study 2, data collection is performed by the principal investigator and trained students. The students will practice data collection prior to the study. It is principal investigator who are the responsible data manager and collect data from the journaling system (CURA). Only data on the above mentioned information will be transferred by the principal investigator into Absalon secured drive (R-drive), when written consent is received. All data will be reviewed by the principal investigator.

A data management agreement with Odsherred City and the University of Copenhagen, has been signed. Data managers in the project are University College Absalon, [name]. [contact]. Data Protection Advisor (DPO): [contact].

The information is collected and processed in accordance with legal authority in Article 6 (1) of the Data Protection Regulation. 1, letter a and Article 9, para. 2, letter al:

The information is processed in accordance with the University College Absalon's privacy policy, including requirements for technical and organizational security - read more here:

<https://www2.phabsalon.dk/studienet/studiehjaelp/informationssikkerhed/politikker-og-vejledninger/privatlivspolitik/>

A data management plan has been prepared in accordance with the guidelines from Good Clinical Practice (GCP) standards, the general data protection regulation with guidance from the University of Copenhagen's faculty's data management and GDPR special consultants.

A data management plan is prepared following the guidelines from Good Clinical Practice standards (28), the Data Protection Regulation and Data Protection Law (29). All data retrieved during the study will be encrypted after collection and will be handled according to Good Clinical Practice standards.

The principal investigator and the students will continuously document all data on each participants. All participant information will be processed according to Data Protection Regulation and Data Protection Law (29). All data is treated pseudonymised, ie. that all participants have an anonymous ID number, which appears when data is processed.

When the project is completed, data is stored on a specially secured research drive with the data controller, ie. Absalon University College for 5 years after the publication of scientific articles.

Relevant anonymized data can only be shared on reasonable request following Data Protection Regulation and Data Protection Law (29).

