#### Primary outcome

Primary outcome is sustained or improved muscle function (30 - second chair stand test (30 s CST), gait speed (10 meters) and hand grip strength (HGS))

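### The principal investigator, who can hardly be unaware of the allocation, and students collect the effort-dependent primary tests, and the protocol provides no assessor masking

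*Protocol*

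**What the plan says.** - **Who measures.** Protocol section 9a states that in sub-study 2 "data collection is performed by the principal investigator and trained students". It adds that "The principal investigator and the students will continuously document all data on each participants" and "All data will be reviewed by the principal investigator". On training it says "The students will practice data collection prior to the study". It does not divide the work by test, home or time point.
- **What is measured.** Under Primary outcome, "Primary outcome is sustained or improved muscle function", made up of the "30 - second chair stand test (30 s CST), gait speed (10 meters) and hand grip strength (HGS"). Table 1 schedules these tests at baseline and 6 months.
- **Who else is there.** Section 6 says: "A nurse at each of the nursing homes is included in the project and will be present during all data collection periods".
- **What the principal investigator knows.** Section 12 has this person inform the homes, staff, relatives and residents, and talk to residents during recruitment. Section 3c allocates whole homes, three to each arm.
- **Safeguards.** Under Sample size calculation, the lottery is drawn by someone outside the project group. Masking of assessors is mentioned nowhere.

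**The concern.** Each of the three primary tests leaves room for the assessor. In the chair stand it is what counts as a complete stand and how strongly the resident is urged on. In gait speed it is when the clock starts and stops. In grip strength it is the encouragement given. An assessor who knows that a home is an intervention home can, without intending to, score or encourage its residents differently.

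Such a shift could act on a whole home at once. With three homes per arm, nothing in the data distinguishes it from a real effect of the programme. More residents per home make the home means more precise but leave the shift where it is. Adjusting for baseline does not remove a shift that arises at the 6-month test.

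Residents and staff cannot realistically be masked to a change in diet and daily activity, so the assessor is the main place where masking is still possible. The independent lottery draw protects the allocation but not the measurement. The matter bears on the results because the protocol powers a comparison between arms, plans ANCOVA for the effect (section 4) and plans a paper on effects (section 13).

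**Working it through.** **1. Reproducing the protocol's own power figure**

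Inputs from Sample size calculation: target difference 1.3 stands, SD of a home 0.42, significance level 0.05 (taken as two-sided, since the protocol does not say), power 80%. Three homes per arm comes from section 3c.

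- SD check: 0.42 × √20 = 1.878, in line with the stated 1.87 per person with 20 residents per home.
- Standard error of the difference between arms: 0.42 × √(2/3) = 0.343.
- Degrees of freedom: 3 + 3 − 2 = 4, so the critical value is 2.776.
- Noncentrality at 1.3 stands: 1.3 / 0.343 = 3.79.
- Power from the noncentral t distribution: 80.6%.

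This matches the stated 80%. A normal approximation would give 96.6%, which does not match, so the t-test on six home means is evidently the method behind the figure.

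**2. What a measurement shift would do in the same test**

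Assume no true effect and a shift *b* favouring the intervention homes. The chance of a significant result is P(|T| > 2.776), where T is noncentral t with 4 degrees of freedom and noncentrality *b* / 0.343.

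| Assumed shift *b* (stands) | Share of the 1.3 target | Noncentrality | Chance of a significant result |
|---|---|---|---|
| 0 | 0% | 0 | 5.0% |
| 0.25 | 19% | 0.73 | 8.8% |
| 0.5 | 38% | 1.46 | 20.4% |
| 0.75 | 58% | 2.19 | 38.8% |
| 1.0 | 77% | 2.92 | 59.6% |

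The documents give no size for assessor bias, so the first column is an assumed range.

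**3. What the text does and does not settle**

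- Section 9a puts the principal investigator among the data collectors, and nothing excludes this person from the primary tests.
- Sections 3c and 12 together make it very unlikely that someone who informs the homes and recruits in them does not know their arm.
- Section 9a provides for a second group of assessors, the students, who practise beforehand. The text does not say whether they know the allocation or take part in the intervention.

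**The case against.** A reader might infer more than the protocol supports.

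- **That the principal investigator leads the intervention.** The protocol does not say so. It describes co-creation with residents, staff and management, lets the homes choose components from a catalog, and names no leader for the PDSA cycles. The point rests only on recruitment and likely knowledge of the arms.
- **That the principal investigator personally performs the primary tests.** Section 9a speaks of data collection jointly. Only the journal data and the data review are given to the principal investigator alone. A scheme in which students do the testing would fit the text, but so would the opposite.
- **That assessment is declared open.** The protocol is silent on masking. Silence still leaves open assessment permitted, and who tests and what they know is trial conduct, which belongs in a protocol rather than in an analysis plan.
- **That the percentages forecast this trial's error rate.** They do not. The shifts are assumed, and 0.42 is a planning value: the text treats 1.87 per person as the largest SD that keeps 80% power. The test is unadjusted where ANCOVA is planned, and only one of the three primary measures is covered.
- **That masking would be free and complete.** The number of students is not given, so it cannot be said that no extra staff are needed. Whole homes are randomised, a change of general diet may be visible on site, and residents and the attending nurse are likely to know the arm.

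There is also a fair argument that a pragmatic feasibility study using action research accepts closeness between researchers and participants. That holds for developing the intervention. It is a weaker reason for leaving the testing unmasked when the protocol also powers and plans a test of effect.

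**Conclusion.** The concern holds in a limited form. The protocol names a person who can hardly be unaware of the allocation, together with students, as collectors of effort-dependent primary data, and it gives no protection against assessor expectation. With three homes per arm, a resulting shift could not be separated from an intervention effect.

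Shifts of about one fifth to three fifths of the target difference would raise a nominal 5% error to between about 9% and 39%. This is a hypothetical sensitivity. It assumes that the shift acts on all intervention homes alike, that home means have SD 0.42, and that the analysis is a two-sided t-test on six home means. Whether any such shift would occur, and how large it would be, cannot be known from the protocol.

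This is an improvement that should be made. It is not a demonstration that the result will be biased.

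**What to change.** Add a paragraph on outcome assessment to the protocol, stating that:

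1. As far as the existing student pool allows, the 6-month chair stand, gait speed and grip tests are done by trained students who took no part in developing or delivering the intervention or its PDSA cycles and who are not told the allocation.
2. The principal investigator does not perform these tests.
3. Each student tests in homes of both arms, so that assessor and arm are not confounded, and uses one fixed instruction script.
4. Attending nurses and residents are asked not to disclose the arm.
5. For each test session, it is recorded whether the assessor became aware of the arm, and the report states how far masking held.

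The cost is the protocol text, scheduling work and more testing load on the students. The sponsor should check that the pool is large enough for about 100 residents in six homes. Masking will be partial, because changes may be visible in intervention homes. The fixed script and testing across both arms remain useful where masking fails, and the awareness record shows how often it did.
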